#### **3.4.1 Extent of Exposure**

Time on treatment in days will be derived from the following formula:

$$\text{Time on treatment (days)} = (\text{date of last dose}) - (\text{date of first dose}) + 1.$$

This calculation does not consider any gaps in exposure caused by the participant missing one or more scheduled doses.

Extent of exposure will be reported for the Safety Set using date of first dose of active treatment.

#### **3.4.2 Adverse events**

The adverse event verbatim descriptions (investigator terms from the CRF) will be classified into medical terminology using the Medical Dictionary for Regulatory Activities (MedDRA). Adverse events will be coded to primary System Organ Class (SOC) and preferred term (PT) using MedDRA, Version 26.0 or newer.

A treatment-emergent adverse event (TEAE) is defined as an AE that had an onset date, or a worsening in severity from baseline (pre-treatment), on or after the first dose of study intervention up to the Safety follow-up visit or Early Termination Visit following study drug discontinuation.

An AE will be considered treatment related if the investigator considers that there is a reasonable possibility that the event may have been caused by the investigation product. If a causal relationship to study intervention is missing for an AE that started on or after the date of first dose of study intervention, causality will not be imputed and a category of “missing” will be included as necessary in incidence summaries. An event with missing onset date will be imputed as treatment-emergent, unless there is other evidence that confirms that the event was not treatment-emergent (e.g., the event end date was prior to the study intervention start date).

---

An AE will be considered serious (SAE) if it meets the definition of SAE given in the protocol Appendix 10.3.2, as recorded on the AE form of the CRF.

If AE have missing or incomplete start or end dates, they will be imputed as described in [Appendix 8.1](#).

The SOCs will be presented in alphabetical order and the PTs will be presented in frequency order for the highest dose of active treatment within each SOC. A participant who reports more than 1 AE in different SOCs will be counted once in the overall total. A participant who reports AEs in different PTs in the same SOC will be counted only once in the SOC total. A participant reporting more than 1 AE in a given PT will be counted only once for that term. In severity and relatedness tables, the most severe or related AE will be counted.

### **3.4.3 Clinical Laboratory Variables**

Laboratory safety assessments will be performed in a central laboratory at each Visit. The hematology, clinical chemistry, urinalysis, and other parameters are outlined in Appendix 2 of the protocol. Laboratory data are to be reported in SI units, except for the blood eosinophils counts which will be reported in conventional units.

For values recorded with a leading greater than or less than ('>', '<') symbol, the reported numeric value will be used for analysis and the value with the symbol will be included in the listings, unless otherwise specified. For example, a value of <0.01 will be analyzed as 0.01 and listed as <0.01.

Absolute values will be compared to the relevant reference range and classified as LNH (low (below normal limit), normal (within normal limits) or high (above normal limit)). The central laboratory ranges will be used for laboratory variables. All absolute values falling outside the reference ranges will be flagged as L (low) or H (high).

### **3.4.4 Vital Signs, Physical Examination Findings, and ECG**

#### **3.4.4.1 Vital Signs**

Predose vital signs (body temperature, blood pressure (BP), heart rate, and respiration rate) will be obtained at each Visit (Week 0 (baseline), 4, 8, 12, and 14). Blood pressure and heart rate will be measured both supine and standing.

Absolute values will be compared to the relevant reference ranges and classified as LNH as defined in [Section 3.4.3](#).

Body mass index (BMI) will be calculated from the height and weight as follows:

$$BMI (kg/m^2) = weight (kg)/(height (m))^2$$

#### **3.4.4.2 Physical Examination**

Complete physical examinations will be performed at Screening only. Each component of

the baseline physical examination will be recorded as normal, abnormal-not clinically significant, or abnormal- clinically significant. Significant changes will be reported as AEs.

#### 3.4.4.3 ECG

ECG assessments are performed at each visit using a triplicate 12-lead ECG machine that automatically calculates the heart rate and measures PR, QRS, QT, and QTc intervals.

Clinically significant findings will be listed and summarized for the Safety Analysis Set.

#### 3.4.5 Other Safety Variables

All women of childbearing potential will take serum/urine pregnancy tests at baseline and Week 14.

Ophthalmic exams will consist of spectral domain optical coherence tomography (SD-OCT) and will evaluate changes to the choroid and to evaluate the fundus. Significant findings will be reported as AEs.

Participants will be observed for suicidal ideation and behavior (SIB) and will take the C-SSRS suicidality assessment at every Visit. Participants with suicidal ideation will be presented in a listing.

### 4 ANALYSIS METHODS

#### 4.1 PARTICIPANT INFORMATION

##### 4.1.1 Disposition of Participants

The number of participants screened and the number and percentage of participants who failed screening and the reasons for screen failure will be summarized for all participants based on data reported on the Screen Failure CRFs. The distribution of the number of randomized participants enrolled by each site will be summarized for each randomized treatment group and overall.

Study Completion: The number and percentage of randomized and treated participants who completed the study and who discontinued from the study will be summarized according to the reason for discontinuation for the mITT, based on data reported on the End of Study CRF.

Completion of Study Treatment: The number and percentage of randomized and treated participants who completed study treatment and who discontinued from study treatment will be summarized according to the reason for discontinuation for the mITT, based on data reported on the End of Treatment CRF.

Reasons for study or treatment discontinuation include:

- Adverse event

- Death
- Pregnancy
- Non-compliance with study drug
- Participant withdrew consent
- Protocol deviation
- Study terminated by Sponsor
- Site terminated by Sponsor
- Lost to follow-up
- Investigator/Physician decision, specify
- Other, specify

#### 4.1.2 Protocol Deviations

Major and minor protocol deviations will be assessed by sponsor personnel following the Protocol Deviation Management Plan. A protocol deviation will be classified as major if there is a potential to significantly impact the completeness, accuracy, and/or reliability of the study data, or affect a participant's rights, safety, or well-being. All protocol deviations will be identified and finalized prior to database lock and treatment unblinding.

The number and percentage of participants with protocol deviations in the mITT Population will be summarized by treatment group and overall. A similar summary will be provided for major PDs due to the COVID-19 pandemic.

A listing of these cases will be provided with the tables, and a listing of all collected protocol deviations will be presented in an appendix listing.

#### 4.1.3 Demographics and baseline characteristics

Demographic and baseline characteristics for the Safety analysis set will be summarized for each treatment group using descriptive statistics. Continuous demographic and baseline variables include age, height, weight, and BMI; categorical variables include sex, age group (< 65 vs ≥ 65), race, and ethnicity.

The status of Parkinson's disease at screening will be summarized according to the categorical variable Modified Hoehn and Yahr stage, and the Montreal Cognitive Assessment total score.

Baseline scores for efficacy assessments will be summarized in the mITT as in Table 4-1:

**Table 4-1 Baseline scores for efficacy assessments**

Assessment	Variable type	Subscales/domains
MDS-UPDRS	Continuous	Part II+III
PDQ-39	Continuous	Total score Mobility Activities of daily living Emotional well-being

		Stigma Social support Cognition Communication Bodily discomfort
PGI-S	Categorical	
CGI-S	Categorical	
MDS-UPDRS	Continuous	Part II Part III Part I
NMSS	Continuous	Total score Cardiovascular Sleep/fatigue Mood/cognition Perceptual problems/hallucinations Attention/memory GI Urinary Sexual function Miscellaneous
CSBM	Continuous	
ESS	Continuous	
SE-ADL	Continuous	
PAGI-SYM	Continuous	Total score Heartburn/regurgitation Postprandial fullness/early satiation Bloating Nausea/vomiting Lower abdominal pain Upper abdominal pain
PAC-QoL	Continuous	Total score Physical discomfort Psychosocial discomfort Treatment satisfaction Worries and discomfort
PAGI-QoL	Continuous	

#### 4.1.4 Medical History

The Medical History will be coded by MedDRA (26.0) or higher version. A participant data listing of medical and surgical history will be provided.

#### 4.1.5 Prior and Concomitant Therapy

All investigator terms for medications recorded on the CRF will be coded using the World Health Organization (WHO) Drug Dictionary Enhanced, March 2018 or newer. The number and percentage of participants who took prior and concomitant medications will be summarized for the Safety population by treatment, Anatomical Therapeutic Chemical (ATC) Classification and WHO Drug preferred term. Prior medications will be defined as medications that stopped prior to the first dose of study drug. Concomitant medications will be defined as medications that (1) with a start date before the first dose of study drug and an end date after the first dose of study drug or ongoing, or (2) with a start date on or after the date of the first dose of study drug up to 14 days following the last dose.

Common PD therapies are listed in Table 4-2. All ATC2 codes of ‘N04’ will be included as anti-Parkinson medication.

Table 4-2 Common PD therapies.

Drug class	Medication
Levodopa	Carbidopa-levodopa Levodopa Duodopa
Dopamine agonists	Pramipexole Rotigotine Apomorphine Ropinirole Stalevo
MAO B inhibitors	Selegiline Rasagiline Safinamide
COMT inhibitors	Entacapone Opicapone Tolcapone
Anticholinergics	Benzatropine Trihexyphenidyl
Mixed mechanism	Amantadine
Adenosine A2A receptor antagonist	Istradefylline

COMT= Catechol-O-methyltransferase; MAO= monoamine oxidase.

Summary tables will be provided for prior PD therapies and prior and concomitant general medications along with supportive listings. Listings will include indication, start date, stop date (or ongoing), and dosage information.

Medications known to be Cytochrome P450 (CYP) 3 A4/5 inhibitors or inducers and those known to be MDR1 or BCRP inhibitors will be listed separately and marked as prior or concomitant (see <https://www.fda.gov/drugs/drug-interactions-labeling/drug-development-and-drug-interactions-table-substrates-inhibitors-and-inducers> for the list of drugs in this category).

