8.1. Discontinuation of Study Intervention

It may be necessary for a participant to permanently discontinue study intervention. If the study intervention is permanently discontinued, efforts will be made to encourage the participant to remain in the study for evaluation according to planned study procedures per SoA. See the SoA for data to be collected at the time of follow-up and for any further evaluations that need to be completed.

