## 2 STATISTICAL CONSIDERATIONS

### 2.1 GENERAL CONSIDERATIONS

SAS® 9.4 or higher will be used to perform all analyses.

All descriptive statistics for continuous variables will be reported using the number of non-missing participants (n), mean, standard deviation (SD), median, minimum and maximum. Categorical variables will be summarized as number and percentage of participants.

The default significance level will be 0.05. p-values will be rounded to three decimal places. If a p-value is less than 0.001 it will be reported as “<0.001”. A p-value greater than 0.999 will be reported as “>0.999”.

Minimum and maximum values will be rounded to the precision of the original value. Means and medians will be rounded to one decimal place greater than the precision of the original value. SD and Confidence Intervals (CI) will be rounded to two decimal places greater than the precision of the original value. Percentages for summarizing categorical data will be rounded to one decimal place.

The number of below the limit of quantitation (BLQ) values, i.e., the n below lower limit of quantification (LLOQ), will be reported for each time point. All study data will be included in study data listings. In general, all data will be listed by time point within

participants. All summary tables will present descriptive statistics for the parameters being analyzed.

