## 4.2.3 Secondary Efficacy Analyses

The efficacy endpoints (as changes from baseline at Week 12) will be evaluated in hierarchical order as described in [Section 2.4](#). The following endpoints will be evaluated:

- Movement Disorder Society-sponsored revision of the Unified Parkinson's Disease Rating Scale (MDS-UPDRS) Parts II + III
- Parkinson's Disease Questionnaire (PDQ-39) summary index
- Patient Global Impression-Severity (PGI-S)
- Clinician Global Impression of Severity (CGI-S)
- MDS-UPDRS Part II
- MDS-UPDRS Part III
- MDS-UPDRS Part I
- Non-Motor Symptom Scale (NMSS) total score
- Complete Spontaneous Bowel Movement Score (CSBM)
- Epworth Sleepiness Scale (ESS) total score
- Schwab and England Activities of Daily Living (SE-ADL) Scale
- Patient Assessment of Upper Gastrointestinal Disorders Severity Index (PAGI-SYM)
- Patient Assessment of Constipation Quality of Life (PAC-QoL)
- Patient Assessment of Gastrointestinal Disorders Severity Quality of Life (PAGI-QoL)

The estimand for the key efficacy endpoint is defined as follows:

- A. Population: Participants with Parkinson's Disease as defined by inclusion/exclusion criteria and in the modified Intent-to-Treat (mITT) population.
- B. Variable: Change from baseline to Week 12 in the MDS-UPDRS Parts II + III score.
- C. Intercurrent Events:
  - a. Premature Discontinuation of Study Treatment
  - b. Initiation of PD Medication for Treatment of Motor Features
- D. Summary: Treatment differences of the least-squared mean (LSM) change from baseline at Week 12 in the MDS-UPDRS Parts II + III summary index between 50, 100, or 200 mg IKT-148009 vs placebo.

For data that are missing due to premature discontinuation of study treatment or initiation of PD medication, no specific imputation will be done. If possible, the collection of data will be continued and used according to the treatment policy strategy. Descriptive statistics for each endpoint will be presented as change from baseline by treatment group and visit.

The differences between the dose levels versus placebo at Week 12 in the continuous secondary endpoints will be estimated using a Mixed Model for Repeated Measures (MMRM) using the mITT Set.

For each endpoint and treatment group, the null hypothesis will be  $H_0: \delta = 0$  and the alternative hypothesis will be  $H_0: \delta \neq 0$ , where  $\delta$  = treatment difference =  $(\bar{x} - \mu)$ .

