### **Prior/concomitant medication**

- The missing day of start date of a therapy will be set to the first day of the month that the event occurred.
- The missing day of end date of a therapy will be set to the last day of the month of the occurrence.
- If the start date of a therapy is missing both the day and month, the onset date will be set to January 1 of the year of onset.
- If the end date of a therapy is missing both the day and month, the date will be set to December 31 of the year of occurrence.
- If the start date of a therapy is null and the end date is not a complete date then the start date will be set to the earlier of the imputed partial end date and the date of the first study visit.

- If the start date of a therapy is null and the end date is a complete date
  - and the end date is after the date of the first study visit then the start date will be set to the date of the first study visit.
  - otherwise the start date will be set to the end date of the therapy.
- If the end date of a therapy is null and the start date is not a complete date then the end date will be set to the study end date.
- If the end date of a therapy is null and the start date is a complete date
  - and the start date is prior to the study end date then the end date will be set to the study end date.
  - otherwise, the end date will be set to the start date of the therapy.

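### SAP 4.1.5 stops counting new medications 14 days after the last dose, so the by-arm count of anti-Parkinson drugs started on study can be too low among early stoppers who stay to Week 12

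*SAP*

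**What the plan says.** SAP 4.1.5 sorts medications into two classes.

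- Prior: "Prior medications will be defined as medications that stopped prior to the first dose of study drug".
- Concomitant, first limb: "with a start date before the first dose of study drug and an end date after the first dose of study drug or ongoing".
- Concomitant, second limb: "with a start date on or after the date of the first dose of study drug up to 14 days following the last dose".

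The same section treats every ATC2 code N04 as anti-Parkinson medication and summarises prior and concomitant medications in the Safety population by treatment, ATC class and preferred term. On output it states: "Summary tables will be provided for prior PD therapies and prior and concomitant general medications along with supportive listings".

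SAP 4.2.3 names two intercurrent events for the key efficacy endpoint: stopping study treatment early, and starting PD medication for motor features. Its handling of later data is: "If possible, the collection of data will be continued and used according to the treatment policy strategy". The MMRM uses changes from baseline at Weeks 4, 8 and 12.

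On stopping study drug, Protocol 8.1 says that "efforts will be made to encourage the participant to remain in the study for evaluation according to planned study procedures per SoA". Protocol 7.6.1 permits PD medication to be started where medically necessary and also encourages those participants to stay in the study.

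**The concern.** The 14-day limit is tied to the last dose, while efficacy follow-up is tied to the visit schedule. For someone who stops study drug early and stays on study, the two come apart. A PD drug started in between was not stopped before the first dose, did not start before it, and did not start within 14 days of the last dose. It therefore fits none of the three definitions and reaches none of the medication tables, although Week 8 or Week 12 scores taken on it can enter the MMRM.

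Under treatment policy, a reader needs to know how many participants in each arm had started anti-Parkinson therapy by Week 12. A difference in MDS-UPDRS Parts II + III in a trial of untreated PD reads differently if one arm was rescued more often. The rule loses part of that count among people who stopped study drug, and stopping may differ by dose. The ocular rule in Protocol 6.3, for example, can halt dosing for everyone at one dose level.

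**Working it through.** The plan gives no figure for this point, and its power statement (SAP 1.3.3) does not bear on it. The check is study-day arithmetic.

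**Inputs.** The cut-off is last dose + 14 days (SAP 4.1.5). Week 12 is scheduled on Day 85 with an analysis window of Days 72 to 91, and the safety follow-up is scheduled on Day 99 (SAP Table 2-1).

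**The rule for a completer.** With the last dose on Day 85, the last counted start is 85 + 14 = Day 99, the scheduled safety follow-up. The rule works here.

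**The rule for an early stopper.** With the last dose on Day L, the last counted start is Day L + 14. The uncounted days are:

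- through Day 85: 85 − (L + 14) = 71 − L, or 0 if negative;
- through Day 91: 91 − (L + 14) = 77 − L, or 0 if negative.

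| Last dose (day) | Last counted start | Uncounted days to Day 85 | Uncounted days to Day 91 |
|---|---|---|---|
| 15 | 29 | 56 (Days 30–85) | 62 |
| 29 | 43 | 42 (Days 44–85) | 48 |
| 57 | 71 | 14 (Days 72–85) | 20 |
| 70 | 84 | 1 (Day 85) | 7 |
| 71 | 85 | 0 | 6 |
| 76 | 90 | 0 | 1 |
| 77 | 91 | 0 | 0 |

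The gap therefore exists for a last dose on or before Day 70 if Week 12 is assessed on Day 85, and on or before Day 76 if it is assessed at the end of its window.

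**Which planned outputs could show a start in the gap.**

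- Prior PD therapy table: no, because the drug did not stop before the first dose.
- Concomitant medication table: no, because it meets neither limb.
- Disposition tables (SAP 4.1.1): no, because starting PD medication is not a listed reason for discontinuation.
- Imputation analysis in SAP 4.2.5: this depends on the first use of PD medication, but it is optional, post hoc and limited to endpoints that reach significance.
- Listings: yes, since SAP 2.1 says "All study data will be included in study data listings".

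**Partial dates (minor).** The medication rule in SAP Appendix 8.1 reads: "The missing day of start date of a therapy will be set to the first day of the month that the event occurred". The adverse-event rule in that appendix instead moves an onset in the first-dose month to the day of first treatment. A PD drug begun on study in that month, with the day missing, would thus be dated before the first dose unless dosing began on the 1st. If it continued past the first dose it is still tabulated under the first concomitant limb, but it looks like existing therapy rather than an initiation.

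**The case against.** The strongest reply is that this is a gap in a descriptive table and nothing more. Most of that stands.

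- **The estimate.** A reader might infer that the Week 12 MMRM result is biased by the window. It is not. SAP 4.2.3 intends post-rescue scores to be included, and widening the window would change the estimate by zero.
- **A size in points.** It is tempting to turn uncounted rescue into a shift in the arm mean. The documents give neither a rescue effect nor a number of such participants. Any such figure would also measure rescue itself, not the window. Entry criteria further limit the numbers by screening out people likely to need anti-parkinsonian treatment (Protocol 6.1 and 6.2).
- **Lost data.** Nothing is lost from the record. Protocol 7.6 requires all medications received during the study to be documented, and the listings carry indication, dates and dosage. With 137 participants enrolled (11 + 126, SAP 1.3.1), the cases could be counted by hand.
- **PD starts in general.** Starts up to the cut-off should appear under N04 by arm in the concomitant table. Only later starts are missed.
- **The prior PD table.** One might suppose eligibility leaves it almost empty. That does not follow. Protocol 6.2 excludes past use of the main drug classes only if it exceeded 28 days or fell within 28 days before screening. It does not name amantadine or anticholinergics, which are in SAP Table 4-2.
- **Visible stopping.** Treatment discontinuation is tabulated with reasons, so uneven stopping would show.

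What the reply does not remove is that the tabulated N04 count follows a stated rule that leaves out part of a named intercurrent event. A reader of the tables would not know that it is incomplete.

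**Conclusion.** The point holds as a reporting defect. For participants with a last dose on or before Day 70 (Day 76 at the end of the Week 12 window) who remain on study, anti-Parkinson drugs started after the cut-off and by the Week 12 assessment are in neither medication class and reach no table. The by-arm N04 count can therefore understate rescue. No dedicated table of PD medication started on study is specified to make up for it.

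The exposed interval is 56, 42 or 14 days for last doses on Days 15, 29 or 57. This takes Week 12 at Day 85 and counts that day. How many participants fall in the interval, and whether they differ by arm, cannot be worked out from the documents. The efficacy estimate, the tests and the data collected are unaffected. What suffers is the interpretation of the treatment-policy result. The partial-date issue is a secondary labelling matter.

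**What to change.** In SAP 4.1.5, for anti-Parkinson drugs (ATC N04 and the levodopa-containing supplements mentioned in Protocol 6.2), count any start from the first dose through the participant's last efficacy assessment, regardless of the last-dose date.

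Add one descriptive table by arm: n (%) who had started by Weeks 4, 8 and 12, split by whether the participant was on or off study drug at the start. Use the mITT set so that the table matches the efficacy analysis. The existing medication tables use the Safety population, which keeps dosed participants randomized before Protocol version 6.1 whom the mITT excludes.

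As a minor addition to Appendix 8.1, for these drugs impute a start with a missing day in the first-dose month to the first-dose date, unless other data show an earlier start. Otherwise an on-study start could be dated before the first dose and left out of the new table.

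The cost is a small wording change and one extra table from data already collected, with no change to any hypothesis, model or participant procedure. If the SAP is already final, the table can be added and noted in the clinical study report, as SAP section 1 provides for deviations.
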